8.3. Exploratory Immunogenicity Analyses

The magnitude, phenotype and percentage of cytokine expressing S protein specific T cells will be summarized at each timepoint by Treatment Group. Mean percentages of CD4 and CD8 T cells expressing cytokines and proportions of responders with 95% CI along with median, minimum, and maximum will be presented by peptide pool stimulation ([Table 183](#), [Table 184](#), [Table 185](#), [Table 186](#), [Table 187](#), [Table 188](#), [Table 189](#), and [Table 190](#)). Distributions of T cell percentages will be graphically displayed (starting with [Figure 698](#) and ending with [Figure 1249](#)).

Individual T-cell responses are shown in [Listing 9](#).

9. SAFETY EVALUATION

Summaries and analysis of safety data will be presented for the Safety Analysis Population.

Solicited AEs will be summarized by severity for each day post vaccination (Days 1-8) for each dose and as the maximum severity over all 8 days. Additionally, solicited AEs will be analyzed by taking the most severe response over the follow-up period and using standard techniques, such as exact confidence intervals (CI), to summarize the proportion of subjects reporting each symptom, any local symptom, and any systemic symptom.

Unsolicited non-serious AEs will be collected from the time of the first vaccination through 28 days after the final vaccination. Unsolicited AEs will be coded by MedDRA for preferred term and system organ class (SOC). SAEs, Protocol Specified AESIs, MAAEs, and NOCMCs will be collected from the time of first vaccination through 12 months after the final vaccination. The numbers of SAEs and MAAEs will be reported by detailed listings showing the event description, MedDRA preferred term and SOC, relevant dates (vaccinations and AEs), severity, relatedness, and outcome for each event. Non-serious unsolicited AEs will be summarized as number and percentage of subjects reporting at least one event in each MedDRA preferred term and SOC, cross tabulated by severity and relationship to study product. Additionally, the proportion of subjects and exact 95% CIs of AEs in aggregate and by MedDRA categories will be computed.

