3. STUDY OBJECTIVES AND ENDPOINTS

3.1. Study Objectives and Endpoints

| OBJECTIVES | ENDPOINTS (OUTCOME MEASURES) |
|--|--|
| Primary | |
| 
 To evaluate the safety and reactogenicity of mRNA-1273 and mRNA-1273.351 vaccines, in naïve individuals. | 
 Frequency and grade of each solicited local and systemic reactogenicity AE during a 7-day follow-up period post each vaccination. Frequency and grade of any unsolicited AEs during the 28-day follow-up period post each vaccination. Frequency of any SAEs, Protocol Specified AESIs, NOCMCs, and MAAEs from the first vaccination through 12 months after the last vaccination. |
| Secondary | |
| 
 To assess humoral immunogenicity of mRNA-1273 and mRNA-1273.351 vaccines, in naïve individuals. | 
 Response rate, and magnitude of SARS-CoV-2-specific antibody binding and neutralization titers in serum samples as assessed via a range of assays at all timepoints. |
| Exploratory | |
| 
 To assess, in at least a subset of samples the innate immune response and B cell response following vaccination. | 
 Magnitude, phenotype, and percentage of innate immune cells and SARS-CoV-2 specific B cells, as measured by flow cytometry, and targeted B cell repertoire analysis at different timepoints post vaccination relative to baseline. |
| 
 To assess, in at least a subset of samples, the SARS-CoV-2 S protein-specific T cell responses. | 
 Magnitude, phenotype, and percentage of cytokine producing S protein-specific T cells, as measured by flow cytometry at different timepoints post vaccination relative to baseline. |

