4.4.6. Treatment Compliance

All subjects are to receive 2 (Arms 2C-H) or 3 (Arms 2A-B) doses of study product administered in the clinic. The number of doses received will be reported in [Table 7](#) (Arms 2A-B) and [Table 8](#) (Arms 2C-H).

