9.3. Adverse Events

When calculating the incidence of adverse events (i.e., on a per subject basis), each subject will only be counted once and any repetitions of adverse events within a subject will be ignored; the denominator will be the total population size. All adverse events reported will be included in the summaries and analyses.

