9.1 Overall Study Design and Plan Description**Table 1: Study Design**

| Arm | Sample Size | First Vaccination | Second Vaccination | | Third Vaccination | |
|-----|-------------|--|--------------------|--|-------------------|----------------------|
| | | Product and Dose | Interval | Product and Dose | Interval | Product and Dose |
| 2A | 15 | 100 mcg mRNA-1273 | 28 days | 100 mcg mRNA-1273 | 28 days | 50 mcg mRNA-1273.351 |
| 2B | 15 | 50 mcg mRNA-1273 | 28 days | 50 mcg mRNA-1273 | 28 days | 50 mcg mRNA-1273.351 |
| 2C | 20 | 100 mcg mRNA-1273.351 | 28 days | 100 mcg mRNA-1273.351 | | None |
| 2D | 20 | 50 mcg mRNA-1273.351 | 28 days | 50 mcg mRNA-1273.351 | | None |
| 2E | 20 | 100 mcg mRNA-1273 | 28 days | 100 mcg mRNA-1273.351 | | None |
| 2F | 20 | 50 mcg mRNA-1273 | 28 days | 50 mcg mRNA-1273.351 | | None |
| 2G | 20 | 50 mcg mRNA-1273 + 50 mcg mRNA-1273.351 | 28 days | 50 mcg mRNA-1273 + 50 mcg mRNA-1273.351 | | None |
| 2H | 20 | 25 mcg mRNA-1273 + 25 mcg mRNA-1273.351 | 28 days | 25 mcg mRNA-1273 + 25 mcg mRNA-1273.351 | | None |

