| [Repeat for all reported PT] | | | | | | | | | | | | | | |
| Arm 2B (N=X) | Any SOC | Any PT | | | | | | | | | | | | |
| | [Repeat for all reported SOC] | Any PT | | | | | | | | | | | | |
| | | [Repeat for all reported PT] | | | | | | | | | | | | |
| Arm 2C (N=X) | Any SOC | Any PT | | | | | | | | | | | | |
| | [Repeat for all reported SOC] | Any PT | | | | | | | | | | | | |
| | | [Repeat for all reported PT] | | | | | | | | | | | | |
| Arm 2D (N=X) | Any SOC | Any PT | | | | | | | | | | | | |
| | [Repeat for all reported SOC] | Any PT | | | | | | | | | | | | |
| | | [Repeat for all reported PT] | | | | | | | | | | | | |
| Arm 2E (N=X) | Any SOC | Any PT | | | | | | | | | | | | |
| | [Repeat for all reported SOC] | Any PT | | | | | | | | | | | | |
| | | [Repeat for all reported PT] | | | | | | | | | | | | |

| | | | Severity | | | | | | | | Relationship to Study Vaccination | | | |
|------------------------------|-------------------------------|------------------------------|---------------|---|------|---|----------|---|--------|---|-----------------------------------|---|---------|---|
| | | | Any Incidence | | Mild | | Moderate | | Severe | | Not Related | | Related | |
| Treatment Group | MedDRA System Organ Class | MedDRA Preferred Term | n | % | n | % | n | % | n | % | n | % | n | % |
| Arm 2F (N=X) | Any SOC | Any PT | | | | | | | | | | | | |
| | [Repeat for all reported SOC] | Any PT | | | | | | | | | | | | |
| | | [Repeat for all reported PT] | | | | | | | | | | | | |
| Arm 2G (N=X) | Any SOC | Any PT | | | | | | | | | | | | |
| | [Repeat for all reported SOC] | Any PT | | | | | | | | | | | | |
| | | [Repeat for all reported PT] | | | | | | | | | | | | |
| Arm 2H (N=X) | Any SOC | Any PT | | | | | | | | | | | | |
| | [Repeat for all reported SOC] | Any PT | | | | | | | | | | | | |
| | | [Repeat for all reported PT] | | | | | | | | | | | | |
| | [Repeat for all reported SOC] | Any PT | | | | | | | | | | | | |
| | [Repeat for all reported PT] | | | | | | | | | | | | | |
| All Subjects (N=X) | Any SOC | Any PT | | | | | | | | | | | | |
| | [Repeat for all reported SOC] | Any PT | | | | | | | | | | | | |
| | | [Repeat for all reported PT] | | | | | | | | | | | | |

Note: N=Number of subjects in the Safety Population.
n=Number of subjects reporting event with the specified SOC.
This table presents number and percentage of subjects. A subject is only counted once per PT and is summarized according to their highest severity and closest relationship.

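### Unsolicited adverse events are an endpoint per vaccination, but the summary tables pool doses: 84 days in Arms 2A-B and 56 days in Arms 2C-H

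*SAP*

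**What the plan says.** The endpoint list in SAP section 3.1 includes "Frequency and grade of any unsolicited AEs during the 28-day follow-up period post each vaccination". Section 9 sets the collection period: "Unsolicited non-serious AEs will be collected from the time of the first vaccination through 28 days after the final vaccination".

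The number of doses differs by arm. Section 4.4.6 states: "All subjects are to receive 2 (Arms 2C-H) or 3 (Arms 2A-B) doses of study product administered in the clinic". Table 1 puts them 28 days apart. The row for Arm 2A reads "2A | 15 | 100 mcg mRNA-1273 | 28 days | 100 mcg mRNA-1273 | 28 days | 50 mcg mRNA-1273.351" and the row for Arm 2C reads "2C | 20 | 100 mcg mRNA-1273.351 | 28 days | 100 mcg mRNA-1273.351 | | None".

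Section 9.3 fixes the incidence rule, with everyone in the analysis population as denominator: "each subject will only be counted once and any repetitions of adverse events within a subject will be ignored; the denominator will be the total". The footnote to Table 411 agrees: "This table presents number and percentage of subjects. A subject is only counted once per PT". Neither rule mentions dose number. For solicited events, in contrast, section 9 asks for a summary per dose, and Tables 390-407 supply it for each arm.

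**The concern.** The endpoint is framed per vaccination, but the planned tables answer a different question: whether a subject had an event at any time from the first dose to 28 days after the last. The chance of at least one background event grows with time observed, and the three-dose arms are observed for longer. A reader who looks across the arms in Tables 387, 388 or 411 would then see a higher percentage in Arms 2A-B even if no vaccine caused any event.

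The pooled count also hides which product came before an event. In Arms 2A, 2B, 2E and 2F the product changes between doses, and Arms 2A-B exist to evaluate a variant vaccine as the third dose. A whole-period percentage cannot separate a third-dose effect from 28 further days of background events.

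**Working it through.** **Inputs.** Doses per arm come from section 4.4.6 and Table 1, the 28-day intervals and arm sizes (15 and 20) from Table 1, and the end of collection from section 9. The SAP gives no unsolicited-event rate, so the rates below are assumptions, shown over a range.

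**1. Collection windows, and the plan's own schedule.**
- Arms 2A-B: doses on Days 1, 29 and 57; collection ends on Day 57 + 28 = 85; length 85 − 1 = 84 days.
- Arms 2C-H: doses on Days 1 and 29; collection ends on Day 29 + 28 = 57; length 57 − 1 = 56 days.
- Ratio: 84 / 56 = 1.5.

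Tables 2 and 3 agree: the last scheduled unsolicited-event collection is Day 85 and Day 57. With the ±2-day windows at the dosing visits, the lengths range over about 80-88 and 54-58 days. The SAP's other figures that bear on safety counts, the detection probabilities in section 5 and Table 4, also reproduce: 1 − 0.8^15 = 96.5%, 1 − 0.8^20 = 98.8%, 1 − 0.97^150 = 99.0%. They are not in question.

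**2. What each table counts.**

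| SAP table | Unit | Arms shown in the mock-up | Split by dose |
|---|---|---|---|
| 387 | subjects | 2A-2H in columns, All Subjects | no |
| 388 | subjects and events | 2A-2H in columns, All Subjects | no |
| 409 | events | 2A-2H stacked in rows, All Subjects | no |
| 410 | events | 2A, 2B, All Subjects | no |
| 411 | subjects | 2A-2H stacked in rows, All Subjects | no |

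**3. Effect on the percentage of subjects.** With a constant background rate and no vaccine effect, the 84-day risk is 1 − (1 − p)^1.5, where p is the 56-day risk.

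| Assumed over 56 days | Over 84 days | Shift in a 15-person arm |
|---|---|---|
| 20% | 28.4% | 0.084 × 15 = 1.3 subjects |
| 30% | 41.4% | 0.114 × 15 = 1.7 subjects |
| 50% | 64.6% | 0.146 × 15 = 2.2 subjects |

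The same model can be written with risk q per 28-day window, comparing 1 − (1 − q)³ with 1 − (1 − q)²:
- q = 1%: 3.0% against 2.0%, ratio 1.49
- q = 10%: 27.1% against 19.0%, ratio 1.43
- q = 50%: 87.5% against 75.0%, ratio 1.17

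The direction is constant. The ratio is largest for rare events and shrinks for common ones.

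**4. Effect on event counts (Tables 409-410).** With an equal expected number of events per window, three windows against two gives 3 / 2 = 1.5 times as many events per subject.

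**5. All Subjects.** With the planned sizes, 30 subjects contribute 84 days and 120 contribute 56. The average is (30 × 84 + 120 × 56) / 150 = 61.6 days, which is the planned length in no arm.

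**6. After the change.** If each cell covers the 28 days after one dose among recipients of that dose, equal risk gives equal percentages: at q = 10%, 10% in every cell.

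**The case against.** The strongest reply is that nothing is lost. With doses exactly 28 days apart, the collection period is the union of the post-dose windows, and section 3.1 may be read as setting the observation period and not a tabulation by dose. It is right that the two sections do not contradict each other on what is collected. But a union counted once per subject gives neither a frequency per vaccination nor equal exposure across arms.

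Several further points stand and limit the concern:
- The randomised treatment is the regimen, so incidence over a whole course is a legitimate description if it is labelled as such.
- No between-arm safety test or difference is planned in section 9.
- Tables 387 and 411 separate related from unrelated events. That helps against background events, though it rests on investigators' judgement in an open-label trial.
- Dose can be traced in part: Table 413 lists moderate and severe non-serious events with dose number, and Table 412 gives days after the associated dose for serious ones. These are listings and yield no frequency. The listing mock-ups and Figures 1274-1275 are not in the text at hand, so their dose content cannot be judged; section 9.3.2 describes those figures by severity and system organ class only.
- The shift is small against the planned precision: the exact 95% interval is 4%-48% for 3/15 and 8%-55% for 4/15.

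A reader might infer that all of these tables set eight arms side by side as percentages. They do not. Table 410 counts events and its mock-up shows only Arms 2A, 2B and All Subjects, and Table 411 stacks the arms in rows. Adjacent columns of percentages occur only in Tables 387 and 388.

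**Conclusion.** The point holds as a matter of descriptive reporting. The unsolicited-event endpoint is stated per vaccination, no summary table reports it that way, and the subject-level tables (387, 388, 411) compare and pool periods that differ by a factor of 1.5. The 84 and 56 days follow from the SAP. The size of the distortion rests on assumed rates and on equal risk in each window: about 1 to 2 subjects per 15-person arm for 56-day risks of 20% to 50%.

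Two stronger readings are tempting and are not supported. One is that the plan makes the three-dose arms look less safe by construction. The expected percentage is shifted upward under the stated assumptions, but the plan draws no formal comparison, shows relatedness separately, and part of any observed excess could be a true third-dose effect. The other is that the 12-month events suffer in the same way. Follow-up there runs to Day 422 against Day 394, so 421 / 393 = 1.07; an assumed 30% becomes 1 − 0.7^1.07 = 32%, about 0.3 of a subject per 15-person arm. That is too small to pursue.

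**What to change.** - Add by-dose versions of Tables 410 and 411, covering events that start within 28 days after dose 1, dose 2 and, in Arms 2A-B, dose 3. The denominator for Table 411 is the subjects given that dose.
- State how an event is assigned when the next dose falls up to 2 days early or late, because the 28-day windows then overlap or leave a gap.
- Add to Table 387 a row for unsolicited events after doses 1 and 2 only: before dose 3 in Arms 2A-B, and through 28 days after dose 2 in Arms 2C-H. This gives all arms a common period.
- Keep the whole-period tables and label them with their collection length: 84 days for Arms 2A-B, 56 days for Arms 2C-H, and mixed for All Subjects.

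The cost is programming and additional table pages. No new data are needed: the SAP's listings already draw on vaccination dates, event dates and dose number.

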9.1. Demographic and Other Baseline Characteristics

Summaries of age, sex, ethnicity, and race will be presented by Treatment Group ([Table 12](#) and [Table 13](#)). Ethnicity is categorized as Hispanic or Latino, or not Hispanic and not Latino. In accordance with NIH reporting policy, subjects may self-designate as belonging to more than one race or may refuse to identify a race, the latter reflected in the CRF as “No” to each racial option. Prior infection status by N-antibody will also be included.

Individual subject listings will be presented for all demographics ([Listing 6](#)).

9.1.1. Prior and Concurrent Medical Conditions

All current illnesses and past pre-existing medical conditions will be MedDRA[®] coded using MedDRA dictionary version 23.0r higher.

Summaries of subjects’ pre-existing medical conditions will be presented by Treatment Group ([Table 14](#)).

Individual subject listings will be presented for all medical conditions ([Listing 7](#)).

9.1.2. Prior and Concomitant Medications

Summaries of medications that were started prior to dosing and continuing at the time of dosing will be presented by WHO Drug Terms 2 and 3 and Treatment Group ([Table 425](#)).

Individual subject listings will be presented for all concomitant medications ([Listing 15](#)).

9.2. Measurements of Treatment Compliance

All subjects are to receive 2 (Arms 2C-H) or 3 (Arms 2A-B) doses of study product administered in the clinic. The number of subjects receiving each dose will be summarized as part of the subject disposition table (Table 7 and Table 8).

9.3. Adverse Events

When calculating the incidence of adverse events (i.e., on a per subject basis), each subject will only be counted once and any repetitions of adverse events within a subject will be ignored; the denominator will be the total population size. All adverse events reported will be included in the summaries and analyses.

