5. SAMPLE SIZE CONSIDERATIONS

Rare AEs are not demonstrable in a clinical study of this size; however, the probabilities of observing one or more AEs given various true event rates are presented in [Table 4](#). With the assumption that all enrolled subjects will likely complete immunizations and safety visits in this relatively short duration study, the following statistical considerations apply. With 15 subjects in Arms 2A and 2B, the chance of observing at least one AE of probability 20% or more is approximately 97%. Therefore, if no AEs of a given type occur in Arms 2A or 2B, we can be relatively confident that they will occur in fewer than 20% of people once the vaccine is implemented. With 20 subjects in each arm (Arms 2C-2H), the chance of observing at least one AE of probability 20% or more is approximately 99%. Therefore, if no AEs of a given type occur in Arms 2C-2H, we can be relatively confident that they will occur in fewer than 20% of people once the vaccine is implemented. With approximately 150 subjects across these eight Arms (2A-2H), the chance of observing at least one AE of probability 3% or more is at least 99%. Therefore, if no AEs of a given type occur across Cohort 2, we can be very confident that any dosage/combination independent event will occur in fewer than 3% of people once the vaccine is implemented.

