6. GENERAL STATISTICAL CONSIDERATIONS

6.1. General Principles

In general, continuous variables will be summarized using the following descriptive statistics: n (non-missing sample size), mean, standard deviation, median, maximum, and minimum. The frequency and percentages (based on the non-missing sample size) of observed levels will be reported for all categorical measures. In general, all data will be listed, sorted by site, treatment, and subject, and when appropriate by visit number within subject. All summary tables will be structured with a column for each treatment and will be annotated with the total population size relevant to that table/cohort, including any missing observations.

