6.4. Missing Data

There are no imputations planned for missing data.

For immunogenicity assays, any values below the lower limit of detection will be imputed as one-half the lower limit of detection for analysis purposes. Any such imputations will be noted in the corresponding analysis.

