9.3.2. Unsolicited Adverse Events

The proportion of subjects reporting at least one unsolicited adverse event will be summarized by MedDRA system organ class and preferred term. Denominators for percentages are the number of subjects who received the vaccination.

Adverse events by subject will be presented in Listing 12.

The following summaries for unsolicited adverse events will be presented by MedDRA system organ class, preferred term, and Treatment Group:

- Subject incidence and total frequency of adverse events ([Table 409](#));
- Summary of severity and relationship to study product ([Table 410](#) and [Table 411](#));
- Listing of Non-Serious, Unsolicited, Moderate or Severe Adverse Events ([Table 412](#));
- Bar chart of frequency of adverse events by severity and MedDRA system organ class ([Figure 1274](#));
- Bar chart of incidence of adverse events by severity and MedDRA system organ class ([Figure 1275](#)).

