9.7. Vital Signs and Physical Evaluations

Vital sign measurements included systolic blood pressure, diastolic blood pressure, pulse, and oral temperature. Vital signs were assessed at Study Days 1, 15, 29, 43, 57, 71, 85, 147, 237, and 422 (Arms 2A-B) and Study Days 1, 15, 29, 43, 57, 119, 209, and 394 (Arms 2C-H). Vital signs will be tabulated by visit and Treatment Group starting with [Table 415](#) and ending with [Table 424](#) ([Listing 13](#)).

Physical Examinations were only to be performed if clinically indicated at Study Days 1, 15, 29, 43, 57, 71, 85, 147, 237, and 422 (Arms 2A-B) and Study Days 1, 15, 29, 43, 57, 119, 209, and 394 (Arms 2C-H). The following body systems will be assessed: Abdomen, Cardiovascular/heart, Extremities, General Appearance, Hepatobiliary/spleen, HEENT, Lymph nodes, Musculoskeletal, Neck, Neurological, Pulmonary/Chest, and Skin ([Listing 14](#)).

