N = Number of subjects in the Safety Population

^aSubjects are counted once for each category regardless of the number of events.

^bA listing of Serious Adverse Events is included in Table 157.

^cAs reported on the Adverse Event eCRF.

Table 388: Serious Adverse Events and Non-Serious Adverse Events Occurring in 5% of Subjects in Any Treatment Group by MedDRA System Organ Class and Preferred Term, and Treatment Group - All Subjects

| Preferred Term | MedDRA System Organ Class | Arm 2A (N=X) | | | Arm 2B (N=X) | | | Arm 2C (N=X) | | | Arm 2D (N=X) | | | Arm 2E (N=X) | | | Arm 2F (N=X) | | | Arm 2G (N=X) | | | Arm 2H (N=X) | | | All Subjects (N=X) | | |
|--|---------------------------|--------------|---|--------|--------------|---|--------|--------------|---|--------|--------------|---|--------|--------------|---|--------|--------------|---|--------|--------------|---|--------|--------------|---|--------|--------------------|---|--------|
| | | n | % | Events | n | % | Events |
| Serious Adverse Events | | | | | | | | | | | | | | | | | | | | | | | | | | | | |
| All | All | x | x | x | x | x | x | x | x | x | x | x | x | x | x | x | x | x | x | x | x | x | x | x | x | x | x | x |
| PT1 | SOC1 | x | x | x | x | x | x | x | x | x | x | x | x | x | x | x | x | x | x | x | x | x | x | x | x | x | x | x |
| Etc. | Etc. | | | | | | | | | | | | | | | | | | | | | | | | | | | |
| Other (Non-serious) Adverse Events | | | | | | | | | | | | | | | | | | | | | | | | | | | | |
| All | All | x | x | x | x | x | x | x | x | x | x | x | x | x | x | x | x | x | x | x | x | x | x | x | x | x | x | x |
| PT1 | SOC1 | x | x | x | x | x | x | x | x | x | x | x | x | x | x | x | x | x | x | x | x | x | x | x | x | x | x | x |
| Etc | Etc | | | | | | | | | | | | | | | | | | | | | | | | | | | |
| N = number of subjects in the Safety Population (number of subjects at risk). n= number of subjects reporting event. Events= total frequency of events reported. | | | | | | | | | | | | | | | | | | | | | | | | | | | | |

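### The 12-month safety events are divided by the full Safety Population and sized as if everyone completes, with no exposure shown; a person-time rate beside the crude percentage would repair this cheaply

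*SAP*

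**What the plan says.** Section 3.1 lists, as one of three primary endpoint components, "Frequency of any SAEs, Protocol Specified AESIs, NOCMCs, and MAAEs from the first vaccination through 12 months after the last vaccination". The other two cover 7 and 28 days after each vaccination. Section 9.7 gives the visit days as "Study Days 1, 15, 29, 43, 57, 71, 85, 147, 237, and 422 (Arms 2A-B"), and ends Arms 2C-H at Day 394. Tables 2 and 3 collect these four event types at every visit up to those days.

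Section 5 introduces its detection probabilities "With the assumption that all enrolled subjects will likely complete immunizations and safety visits in this relatively short duration study". It does not separate the short endpoint components from the long one.

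For incidence per subject, Section 9.3 says "the denominator will be the total population size", and adds that all reported adverse events enter the summaries. Section 9.3.2 says of unsolicited events: "Denominators for percentages are the number of subjects who received the vaccination". Table 387 prints per-arm percentages on the Safety Population in rows for SAEs, MAAEs and NOCMCs. It has no AESI row. Table 388 carries the footnote "N = number of subjects in the Safety Population (number of subjects at risk").

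Early termination is foreseen: Tables 2 and 3 have an early termination visit, Tables 7 and 8 count terminations by arm, and Listing 2 gives the reasons. The text at hand plans no person-time, censoring or count of subjects still followed for the 12-month events.

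**The concern.** The completion assumption suits events collected for 7 or 28 days after a dose. It fits a window of 13 to 14 months less well. A subject in Arms 2C-H last seen at Day 57 contributes 337 further days (394 − 57) in which no event can be recorded, yet stays whole in the denominator. The resulting percentage can only err downwards as an estimate of 12-month risk, by an amount that depends on each arm's losses, and no exposure figure stands beside it. The label in Table 388 makes this harder to see, because the Safety N is no longer the number at risk late in follow-up once anyone has left.

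The reading as a risk is not far-fetched. Section 5 itself moves from no observed events to a statement about the rate in people once the vaccine is in use, and that step needs the window to be fully observed.

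**Working it through.** **Window length.** 394 / 30.4375 = 12.9 months (Arms 2C-H); 422 / 30.4375 = 13.9 months (Arms 2A-B).

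**The plan's own figures.** Section 5 and Table 4 follow from P(at least one event) = 1 − (1 − p)^n with full follow-up:

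- n = 15, p = 20%: 1 − 0.80^15 = 96.5% (Table 4: 96.5)
- n = 20, p = 20%: 1 − 0.80^20 = 98.8% (Table 4: 98.8)
- n = 150, p = 3%: 1 − 0.97^150 = 98.96% (Table 4: 99.0)

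All 30 cells of Table 4 reproduce. The arithmetic is right on its own assumption.

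**Effect of early exit on the crude percentage.** The SAP gives no dropout rate, so the share d is an assumption. Take a true full-window risk p and a constant hazard, with cumulative hazard h = −ln(1 − p). The planned proportion is on average (1 − d)p + d·m, where m is the risk accrued before exit:

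- exits spread evenly over the window: m = 1 − p/h
- all exits at Day 57 of 394: m = 1 − exp(−h × 57/394)
- all exits at the very start: m = 0

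For p = 30%: h = 0.357, so m = 1 − 0.30/0.357 = 0.159 (even) or 0.050 (Day 57). At d = 10% with even exit: 0.90 × 0.30 + 0.10 × 0.159 = 0.286.

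| Loss d | Even exit | All at Day 57 | All at start |
|---|---|---|---|
| 10% | 28.6% | 27.5% | 27.0% |
| 20% | 27.2% | 25.0% | 24.0% |
| 30% | 25.8% | 22.5% | 21.0% |

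For p = 10%, even exit gives 9.5%, 9.0% and 8.5% at the same losses. The relative shortfall is close to d/2 with even exit and equals d when everyone leaves at the start.

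In subjects, at p = 30% and 10% even loss: 15 × (0.300 − 0.286) = 0.2 and 20 × 0.014 = 0.3. At 30% even loss it is about 0.6 and 0.8. Only the harsher pattern reaches a whole subject: 20% loss at Day 57 gives 20 × (0.300 − 0.250) = 1.0 in an arm of 20.

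**Effect on the detection probabilities.** Put the reduced proportion into 1 − (1 − p)^n:

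| Claim | Full follow-up | 10% even | 30% even | 30% at start |
|---|---|---|---|---|
| n = 15, 20% | 96.5% | 95.8% | 94.0% | 89.6% |
| n = 20, 20% | 98.8% | 98.5% | 97.7% | 95.1% |
| n = 150, 3% | 99.0% | 98.7% | 97.9% | 95.9% |

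**The case against.** The strongest reply is that the endpoint is an observed frequency, and for that the number of subjects with a reported event over the number vaccinated is exact. Section 9 reports SAEs and MAAEs by detailed listings, so the percentages in Tables 387 and 388 are secondary displays. In arms of 15 to 20 a correction below one subject is small beside sampling error: the exact 95% interval for 6 of 20 is 11.9% to 54.3%. Most of this stands. It is a reason to keep the crude percentage, but it does not explain why no exposure is shown beside it.

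Several stronger readings are tempting and are not supported:

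- *Early leavers count as event-free.* They do not. Section 9.3 keeps every reported event, and Tables 2 and 3 collect these events at the early termination visit. Only the time after last contact is affected.
- *The percentages are biased as planned.* That depends on dropout. With none, there is no shortfall.
- *Arms with more losses will be judged safer.* No between-arm safety test appears in the text at hand, and Tables 7 and 8 show terminations by arm.
- *The denominator contradicts Sections 6.1 and 6.4.* Section 6.1 states that "The frequency and percentages (based on the non-missing sample size) of observed levels will be reported for all categorical measures", but as a general principle; Sections 9.3 and 9.3.2 are the specific adverse event rules. Section 6.4 says "There are no imputations planned for missing data", and an event that was never reported is not a recorded missing value.
- *The conclusions in Section 5 fail once anyone leaves.* With one of 15 subjects wholly lost, detection at a 20% rate is still 1 − 0.80^14 = 95.6%.

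**Conclusion.** The point holds as a modest improvement. The plan applies one completion assumption and one denominator to endpoint components that differ greatly in length, and for the longest one it shows no exposure. If subjects leave early, the crude percentage understates 12-month risk by about half the dropout share under even exit and by up to the full share under very early exit. At 10% even loss that is 28.6% for a true 30%, under one subject per arm, and the 20% and 3% claims in Section 5 move by less than one percentage point. These sizes rest on an assumed dropout share, a constant hazard and the stated exit patterns. Table 4 is correctly computed and is an upper limit for the 12-month events.

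**What to change.** Keep the crude percentages and the listings. Then:

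1. In Section 9.3 and Table 387, for SAEs, MAAEs and NOCMCs, and in a new AESI row, add by arm the number of first events per person-year with an exact Poisson 95% interval. Count time from first vaccination to first event or last safety contact. Show the person-time or the number still followed.
2. In Table 388, stop labelling the Safety N as the number at risk for these events.
3. In Section 5, limit the full-completion assumption to the 7-day and 28-day endpoints, and state that Table 4 is an upper limit for the 12-month endpoint.

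The cost is SAP wording and a few table rows. Section 9.4 already calls for onset dates, and the visit schedule gives the last safety contact, so trial conduct does not change. The intervals will be wide where events are few, and the stated detection probability becomes slightly less favourable. Replacing the crude percentage as the main estimate is not needed.
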